3.1.5 Re-challenge in Dose Escalation (Part C) and Cohort Expansion (Part D)

If subjects progress during the clinical follow-up period or the survival follow-up period, they could further receive therapy with relatlimab alone or in combination therapy (Re-challenge) as long as the risk:benefit ratio is considered favorable by the Investigator and the Medical Monitor and the following eligibility criteria are met: 1) Subject has confirmed disease progression; 2) Subject has not experienced relatlimab related adverse events leading to permanent discontinuation. The original dose and schedule of therapy and protocol rules will apply. Thus subjects could receive therapy for up to [REDACTED] additional eight-week cycles. Subjects who are re-challenged and who subsequently have an objective response will not be included in the primary analysis of efficacy. Responses to re-challenge will be evaluated in a separate analysis. Subjects will not be re-challenged a second time.

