8.2 Populations for Analyses

- **All Enrolled Subjects:** All subjects who signed an informed consent form and were registered into the IVRS.
- **All Treated Subjects:** All subjects who received at least one dose of study medication. This is the primary population for safety and efficacy analyses.
- **Response-Evaluable Subjects:** All treated subjects with measurable disease at baseline and one of the following: 1) at least one post-baseline tumor assessment, 2) clinical progression, or 3) death (if death occurred within 135 days after last relatlimab dose).
- **Pharmacokinetic Subjects:** All subjects who received at least one dose of relatlimab or nivolumab and have evaluable plasma/serum concentration data.
- **Immunogenicity Subjects:** All treated subjects with relatlimab or nivolumab who have baseline and at least one post baseline immunogenicity assessment.
- **Biomarker Subjects:** All treated subjects with available biomarker data.

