8.3 Endpoints

8.3.1 Primary Endpoint(s)

The primary endpoint of this Phase 1 study is safety as measured at the study level by the rate of AEs, SAEs, AEs leading to discontinuation, deaths, and laboratory abnormalities, assessed during treatment and for up to 135 days after the last treatment. All subjects who receive at least one dose of relatlimab alone or in combination with nivolumab will be analyzed for safety.

Co-primary endpoint in Part D is objective response rate (ORR) and duration of response (DOR) (see [Section 8.3.2.3](#) for details).

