8.3.2.3 Efficacy

All efficacy analyses will be based on the all treated analysis population except otherwise stated. Co-primary, secondary and exploratory efficacy endpoints for Part D subjects are as follows:

Objective Response Rate (ORR)

ORR based on investigator assessment, according to the applicable criteria based on tumor type, will be co-primary endpoint in Part D. For the NHL and HL subjects, the ORR will be based on the IWG (2007) response criteria. In addition to the primary ORR endpoint, an exploratory endpoint of ORR based on the Lugano (2014) response criteria in the NHL and HL subjects in Part D will be assessed. For the Lugano criteria, response is defined as CMR and PMR.

Duration of Objective Response (DOR)

DOR is defined as the time between the date of first documented response (CR or PR) to the date of the first objectively documented progression as per criteria relevant to each disease type in Part D (Appendices 1, 2, and 6), or death due to any cause, whichever occurs first. For subjects who neither progress nor die, DOR will be censored on the date of their last tumor assessment. Subjects who start subsequent therapy without a prior reported progression will be censored at the last tumor assessments prior to initiation of the subsequent anticancer therapy. This endpoint will only be evaluated in subjects with objective response of CR or PR. DOR will be evaluated based on investigator assessments. DOR is a co-primary endpoint in Part D. DOR based on the Lugano (2014) response criteria, response defined as CMR or PMR, will be assessed for the NHL/HL subjects in Part D as an exploratory endpoint.

Complete Response (CR) Rate and Duration

The CR rate is defined as the number of subjects with a best overall response (BOR) of CR according to the applicable criteria based on tumor type, based on IWG criteria for NHL and HL subjects, divided by the number of treated subjects. The duration of CR (DoCR) will only be evaluated in subjects with BOR of CR and is defined as the time from first documentation of CR (the date of first negative FDG-PET scan) to the date of initial objectively documented progression as determined using the applicable criteria based on tumor type or death due to any cause, whichever occurs first. Censoring will be applied as per DOR definition. CR rate and DoCR will be evaluated based on investigator assessments. CR rate is an exploratory endpoint in this study.

Progression Free Survival (PFS) Rate

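### Removing subjects who respond after re-challenge makes the Part D co-primary ORR and DOR population depend on a post-baseline outcome and conflicts with the all-treated definition

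*Combined protocol and SAP*

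**What the plan says.** Section 3.1.5 allows a second period of treatment: "If subjects progress during the clinical follow-up period or the survival follow-up period", subjects may receive study therapy again if the benefit-risk balance is judged favourable and two conditions hold. The first is "1) Subject has confirmed disease progression"; the second is that no relatlimab-related adverse event led to permanent discontinuation. Response in the original course is not a condition.

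On analysis, the section says "Subjects who are re-challenged and who subsequently have an objective response will not be included in the primary analysis of efficacy", followed by "Responses to re-challenge will be evaluated in a separate analysis". The synopsis, under its re-challenge heading, carries the same two sentences.

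Section 8.2 defines All Treated Subjects as "All subjects who received at least one dose of study medication. This is the primary population for safety and efficacy analyses". It makes no exception for re-challenge. Section 8.3.2.3 opens with "All efficacy analyses will be based on the all treated analysis population except otherwise stated". Section 8.3.1 makes ORR and DOR co-primary in Part D, and Section 8.4.2 specifies Clopper-Pearson intervals for proportions and Kaplan-Meier estimation for DOR.

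**The concern.** The exclusion attaches to the subject and is triggered by an outcome observed after baseline, after the original course and after a further course of treatment. A subject who leaves the analysis takes along the original-course result, whichever way it went. A re-challenged subject who does not respond keeps that result in.

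A single-arm response rate has a clear meaning only if the denominator is fixed by entry to treatment. Here it would be fixed by later success. The two efficacy endpoints that Part D is meant to estimate would then describe a selected subset, and the exact binomial interval would be computed on that subset. Re-challenge may also start during survival follow-up, which Section 3.1 runs to 5 years from first dose in HL subjects. A subject counted at one data cut could therefore disappear at a later one without any change in the original-course data.

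**Working it through.** **There is no stated figure to reproduce.** Part D cohort sizes, historic and target rates, and error rates are redacted, and the number expected to be re-challenged is not given. The check compares the sections and then illustrates the effect with assumed numbers.

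**1. Who leaves the analysis under the sentence as worded**

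| Treated subject | Section 3.1.5 and synopsis | Section 8.2 |
|---|---|---|
| Never re-challenged | in | in |
| Re-challenged, no response to re-challenge | in | in |
| Re-challenged, response to re-challenge | out | in |

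The two rules differ only in the last row. Entry to that row needs two post-baseline events: confirmed progression in follow-up, then response to re-treatment.

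**2. Which text governs.** Section 8.2 has no exception, so it conflicts with Section 3.1.5. Section 8.3.2.3 allows exceptions stated elsewhere, so Section 3.1.5 can be read as one, and the exclusion would then take effect. The IWG-based definitions of ORR, DOR and CR rate in Section 8.3.2.3 do not mention re-challenge, and nothing there says that the subject stays in with the original-course outcome.

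**3. Effect on ORR.** Let x of n treated subjects respond in the original course, and let k be removed.

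- All k responded in the original course: ORR = (x − k)/(n − k), which is lower than x/n.
- None of the k responded in the original course: ORR = x/(n − k), which is higher than x/n.

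With n = 20, x = 8, k = 2 (assumed): 8/20 = 40.0% becomes (8 − 2)/(20 − 2) = 6/18 = 33.3%, or 8/18 = 44.4%.

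Other assumed inputs, with k = 3:

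| All treated | Removed had responded originally | Removed had not responded originally |
|---|---|---|
| 4/20 = 20.0% | 1/17 = 5.9% | 4/17 = 23.5% |
| 10/20 = 50.0% | 7/17 = 41.2% | 10/17 = 58.8% |
| 16/20 = 80.0% | 13/17 = 76.5% | 16/17 = 94.1% |
| 8/40 = 20.0% | 5/37 = 13.5% | 8/37 = 21.6% |
| 20/40 = 50.0% | 17/37 = 45.9% | 20/37 = 54.1% |
| 32/40 = 80.0% | 29/37 = 78.4% | 32/37 = 86.5% |

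The largest shift with three removed is 14.1 points at n = 20 and 6.5 points at n = 40. For scale, the Clopper-Pearson interval for 10/20 is 27.2% to 72.8%. With one removed, 10/20 moves only to 9/19 = 47.4% or 10/19 = 52.6%.

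**4. Effect on DOR.** Every removed original-course responder has progressed, so each removal deletes an observed event. Take 20 responders, with progressions at months 2, 4, …, 24 (12 events) and 8 censored at month 36 (assumed). No one is censored before month 24, so the Kaplan-Meier estimate there is 8/20 = 0.40, and the median is 20 months.

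- Remove the events at months 18, 20 and 22: 9 events remain; month-24 estimate 8/17 = 0.47; median 24 months.
- Remove the events at months 20, 22 and 24: 9 events remain; month-24 estimate 8/17 = 0.47; median 18 months.

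The curve rises after the deleted event times because the event is gone. Before them it falls slightly, because one fewer subject is at risk. Late estimates therefore go up, but the median can go either way.

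**The case against.** The best defence is that the sponsor meant something milder: a response to re-challenge should not turn an original-course non-responder into a responder. The next sentence, "Responses to re-challenge will be evaluated in a separate analysis", fits that reading. So does the CR rate in Section 8.3.2.3, which is divided by the number treated. DOR ends at first documented progression, so it is already settled before re-challenge. The Lugano PFS definition in Section 8.3.3.3 disregards deaths after retreatment, a rule that would be needed only if retreated subjects stay in.

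This makes the milder intent plausible, but it does not put it in the text. The plan speaks of subjects in the excluding sentence and of responses in the next. It repeats the wording in the synopsis, and no IWG-based definition limits assessments to the original course. A programmer following the sentence would drop the subject.

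It is also fair to say that Section 8.3.2.3 does not itself contradict the exclusion, because it allows stated exceptions. The clear conflict is with Section 8.2.

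Finally, re-challenge is for selected cases, Section 1.2 says that no hypotheses are formally evaluated, and the two-stage design is given as an example only. These points limit the consequence. They do not make the population well defined.

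**Conclusion.** The sentence should be corrected before the Part D primary efficacy analysis. As written, it selects the co-primary ORR and DOR population on a later outcome and disagrees with Section 8.2. The size of the effect cannot be determined from the documents. The figures above rest on assumed cohort sizes, response rates and numbers removed, and the practical effect may be small if few subjects are re-challenged and respond.

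A reader might infer more than the documents support:

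- **That the ORR is biased downward** because those removed are mainly original-course responders who stopped without progression. Section 3.1.5 requires neither, and Section 4.3.5 also lets therapy be re-initiated case by case after discontinuation. The direction is open.
- **That DOR is biased upward throughout.** Only the late part of the curve must rise; the median need not.
- **That a false-positive rate is inflated.** The plan tests no formal hypothesis, so the damage is to the estimates and their intervals.

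**What to change.** Replace the excluding sentence and the one after it, in both Section 3.1.5 and the synopsis, with:

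> All treated subjects remain in the primary efficacy analysis, with BOR, ORR, CR rate and DOR based on assessments from the original treatment course, before the first re-challenge dose and before any subsequent anticancer therapy. Responses after re-challenge do not count in the primary analysis and are summarised separately.

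This brings both places into line with Section 8.2 and leaves the ORR at x/n. Do not use this change to add a cut-off at first progression for BOR or ORR. Section 4.3.4 permits treatment beyond initial progression, and how responses in that period count is a separate question.

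The cost is the same short text change in two places, plus matching analysis programming. No new data are needed and no treatment rule changes.

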3.1.6 Dose-Limiting Toxicities

For the purpose of guiding decisions regarding dose escalation in Part A, dose-limiting toxicity (DLT) will be determined based on the incidence, intensity, and duration of AEs that are related to study drug and that occur within 8 weeks of initiation of study drug (ie, the DLT evaluation interval which begins on the first day of treatment and ends on Day [REDACTED] of the first cycle).

For the purpose of guiding decision in combination dose escalation in Part C, dose-limiting toxicity (DLT) will be determined based on the incidence, intensity, and duration of AEs that are related to study drug and that occur within 4 weeks of initiation of study drug (ie, the DLT evaluation interval which begins on the first day of treatment and ends on Day [REDACTED] of the first cycle).

The severity of AEs will be graded according to National Cancer Institute (NCI) Common Terminology Criteria for Adverse Events (CTCAE) v4.0.

For the purpose of subject management, DLTs that occur at any time, whether during dose escalation (Part A or C) or cohort expansion (Part B or D) will result in study drug being held pending evaluation of the event's relatedness to study drug in accordance with [Section 4.3.2](#). Subjects must meet criteria for re-treatment prior to re-initiation of study treatment (see [Section 4.3.3](#)).

3.1.6.1 Rationale for 4-week DLT Period in Part C

The identification of acute dose limiting toxicities that occur after administration of a study drug is crucial for the safety of the patients enrolled in a clinical trial. The length of the DLT is usually established based on the availability of pre-clinical data. When clinical data are available, the risk/benefit evaluation used to define the appropriate DLT period must be reassessed and should incorporate a critical analysis of all, clinical and pre-clinical data.

In Part C, the DLT period will be reduced from [REDACTED] weeks to [REDACTED] weeks in light of the availability of preliminary clinical data from the 2 ongoing clinical studies. This decision was made after reviewing the incidence of severe adverse event in monotherapy and in combination between Weeks [REDACTED] to [REDACTED] and after Week [REDACTED] and the effect of a prolonged DLT on a population with advance cancers, as reported below.

Correlation between AEs and duration of treatment

The safety profile of relatlimab as monotherapy is well manageable and generally consistent across the 2 ongoing clinical studies with no MTD reached at the [REDACTED] doses tested, up to [REDACTED] mg in dose escalation monotherapy. Only [REDACTED] subject experienced a related high-grade AE (asymptomatic Grade 3 lipase increased), [REDACTED] days post the first administration of the study drug in CA224020. There were no related SAEs reported in the monotherapy in either study.

A preliminary analysis of the clinical data from the combination arm of Study CA224020 in which [REDACTED] subjects were treated with relatlimab in combination with nivolumab showed that there was no relationship between the incidence, severity, or causality of AEs and the dose level of study drugs. Seven subjects received [REDACTED] mg relatlimab/[REDACTED] mg nivolumab, nine subjects were treated with [REDACTED] mg relatlimab/[REDACTED] mg nivolumab and eight subjects received [REDACTED] mg relatlimab/[REDACTED] mg nivolumab.

The target populations for phase 1/2a oncology studies are characterized by a high frequency of patients with advanced stage disease. As a consequence, a relevant group of patients will progress rapidly after initiation of study drug. Across the 2 ongoing studies with relatlimab, administered as monotherapy or in combination with nivolumab, [REDACTED] of the subjects enrolled in dose escalation cohorts experienced disease progression between Weeks 4 and 8 of the DLT period while only [REDACTED] of the subjects progressed between Weeks 1 and 4. It is important to note that a subject that progresses during the DLT period is no longer evaluable for the purposes of safety adjudication and a new replacement subject must be enrolled at the same dose in order to complete the safety evaluation at that dose level. As a consequence, to date, nine additional patients have been exposed to safe but clinical suboptimal doses of relatlimab alone or in combination with nivolumab.

In summary, the review of the safety data from the 2 ongoing studies strongly suggests that a 4 weeks DLT period will provide an appropriate window to capture the acute, treatment related AEs and to ensure the safety of the patients enrolled in this clinical trial. Furthermore will limit the number of patients exposed to safe but suboptimal doses of the drugs due to progressive disease between Weeks 4 and 8.

Hepatic, non-hematologic, and hematologic DLTs are defined separately as outlined below.

Hepatic DLT

Any of the following drug-related events will be considered a hepatic DLT:

- Alanine aminotransferase (ALT) or aspartate aminotransferase (AST) > 8 × ULN, regardless of duration.

- ALT or AST $> 5 \times$ and $\leq 8 \times$ ULN, that fails to return to \leq Grade 1 within 2 weeks despite medical intervention.
- Total bilirubin $> 5 \times$ ULN.
- ALT or AST $> 3 \times$ ULN and concurrent total bilirubin $> 2 \times$ ULN.

Non-Hematologic DLT

Any of the following drug-related events will be considered a non-hematologic DLT:

- Grade 2 immune related-eye pain or reduction in visual acuity that requires systemic treatment, or
- Grade 2 eye pain or reduction in visual acuity that does not respond to topical therapy and that does not improve to Grade 1 within 2 weeks of initiation of topical therapy, or
- \geq Grade 3 non-hepatic or non-hematologic toxicity with the exceptions noted below.

The following Grade 3 or 4 non-hematologic events **will not** be considered DLTs:

- Grade 3 electrolyte abnormality (and grade 4 hyperglycemia) that lasts < 72 hours, is not clinically complicated, and resolves spontaneously or responds to conventional medical intervention.
- Grade 3 or 4 increase in amylase or lipase that is not associated with symptoms, clinical manifestations, or radiographic evidence of pancreatitis.
- Grade 3 nausea or vomiting that lasts < 48 hours and resolves to \leq Grade 1 either spontaneously or with conventional medical intervention.
- Grade 3 diarrhea that lasts < 24 hours, does not result in hospitalization, and resolves to \leq Grade 1 either spontaneously or with conventional medical intervention.
- Grade 3 or 4 fever that lasts < 72 hours and is not associated with hemodynamic compromise (including hypotension, or clinical or laboratory evidence of end organ perfusion impairment).
- Grade 3 endocrinopathy that is well controlled by hormone replacement.
- Grade 3 tumor flare (defined as pain, irritation, or rash that localizes to sites of known or suspected tumor).
- Grade 3 fatigue for less than 7 days.
- Grade 3 rash meeting the following criteria: 1) improves to grade 1 within 2 weeks, 2) does not limit self-care, and 3) is not associated with infection.
- Grade 3 troponin not associated with any other sign of cardiac toxicity (as determined by a cardiac evaluation).

Hematologic DLT

Any of the following drug-related events will be considered a hematologic DLT:

- Grade 4 anemia.

- Grade 4 febrile neutropenia of any duration.
- Grade 4 neutropenia that does not resolve to Grade 3 or less within 5 days of initiation of granulocyte colony stimulating factor (G-CSF).
- Platelet transfusion or a platelet count < 10,000/ μ L.
- Grade 3 thrombocytopenia associated with clinically significant bleeding.
- Grade 3 hemolysis.

In Part A, subjects who receive at least 1 dose of relatlimab during the 8-week evaluation interval will be considered evaluable for DLT determination. In Part C, subjects who receive at least 2 doses of relatlimab and nivolumab during the 4-week evaluation interval will be considered evaluable for DLT determination. In the event that study drug cannot be administered at a scheduled visit during the DLT evaluation interval, it must be administered as soon as possible. If the delay is between 1 and 7 days, the procedures at the originally scheduled visit should be performed and subjects will be considered evaluable for DLT determination. If the delay is more than 7 days, the dose will be considered missed and will not be replaced. Subjects with a delay of more than 7 days will not be considered evaluable for DLT determination. Unevaluable subjects may be replaced at the same dose level. Subjects who miss a dose during the DLT evaluation period may continue on treatment if the subject does not otherwise meet the criteria for permanent discontinuation in [Section 4.3.5](#).

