3.1.1 Part A - Dose Escalation

In Part A, a 3 + 3 + 3 design will be used to assess the safety of relatlimab. The dose levels evaluated during dose escalation are provided in Table 3.1.1-1. Dose escalation rules are outlined below. Three subjects will initially be treated in each dose cohort; in Dose Cohort 1, the first 3 subjects will be designated as sentinel subjects and will begin treatment at least 5 days apart. Subjects in subsequent cohorts will not be required to observe the 5-day interval between treatment start dates.

Dose escalation will be based on the number of DLTs experienced during the DLT evaluation interval as determined by the Medical Monitor and Investigators (see [Section 3.1.3](#) for DLT criteria). The DLT evaluation interval begins on the first day of treatment and continues for 8 weeks, ie, through Day [REDACTED] of the first cycle. Subjects who receive at least 1 dose of study drug during the 8-week evaluation interval will be considered evaluable for DLT determination. In consultation with Investigators, the Sponsor has the option to investigate dose levels intermediate to those defined in the protocol.

Dose escalation in Part A (Table 3.1.1-1) will proceed as follows:

- If none of the first [REDACTED] evaluable subjects in a dose cohort experiences a DLT within the DLT evaluation interval, then the next [REDACTED] subjects will be treated at the next higher dose cohort.
- If 1 of the first [REDACTED] evaluable subjects in a cohort experiences a DLT within the DLT evaluation interval, then [REDACTED] additional subjects will be treated in that dose cohort.
 - If no more than [REDACTED] of the first [REDACTED] evaluable subjects experiences a DLT during the DLT evaluation interval, then the next [REDACTED] subjects will be enrolled at the next higher dose cohort.
 - If [REDACTED] of the first [REDACTED] evaluable subjects in a cohort experience a DLT, that cohort will be expanded to [REDACTED] evaluable subjects.
- If \geq [REDACTED] of the first [REDACTED] evaluable subjects, \geq [REDACTED] of the first [REDACTED] evaluable subjects, or \geq [REDACTED] of the first [REDACTED] evaluable subjects in a cohort experience a DLT within the DLT evaluation interval, that dose level will have exceeded the MTD and dose escalation will be terminated.

Table 3.1.1-1: Dose Escalation Schedule for Part A - Relatlimab Monotherapy

Dose Cohort Number	Relatlimab Dose (IV; mg)	Total Subjects
1	[REDACTED]	n = approximately [REDACTED]

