3.4 Concomitant Treatments

3.4.1 Prohibited and/or Restricted Treatments

The following medications are prohibited during the study:

- Immunosuppressive agents unless they are utilized to treat an AE or as specified in [Section 3.4.3](#).
- Concurrent administration of any anticancer therapies (investigational or approved) with the exception of subjects in the survival period of the study.
- Use of allergen hyposensitization therapy.
- Use of growth factors unless prior discussion and agreement with BMS Medical Monitor.
- Use of cannabis or other recreational drugs.
- Any live / attenuated vaccine (eg, varicella, zoster, yellow fever, rotavirus, oral polio and measles, mumps, rubella [MMR]) during treatment and until 100 days post last dose.

Palliative radiotherapy is permitted only under certain conditions as described in Section 3.4.3.

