4.3.5 Guidelines for Permanent Discontinuation

Subjects meeting any of the following criteria will be required to permanently discontinue all study drug(s) (relatlimab in Part A and B; relatlimab and nivolumab in Parts C and D):

- Any Grade 3 non-skin, drug-related adverse event lasting > 7 days or recurs, with the following exceptions for laboratory abnormalities, drug-related uveitis, pneumonitis, bronchospasm, hypersensitivity reactions, infusion reactions, and endocrinopathies.
- Grade 3 drug-related myocarditis, uveitis, pneumonitis, bronchospasm, or hypersensitivity reaction of any duration.
- Grade 3 infusion reaction that does not return to Grade 1 in 6 hours or less.
- Any Grade 2 drug-related uveitis, eye pain or blurred vision that does not respond to topical therapy and does not improve to Grade 1 severity within the re-treatment period OR requires systemic treatment.
- Any Grade 4 drug-related AE or laboratory abnormality (including but not limited to creatinine, AST, ALT, or Total Bilirubin), except for the following events which do not require discontinuation:
 - Isolated Grade 4 electrolyte imbalances/abnormalities that are not associated with clinical sequelae and are corrected with supplementation/appropriate management within 72 hours of their onset.
 - Grade 4 neutropenia ≤ 7 days in duration.
 - Grade 4 lymphopenia or leukopenia.
 - Isolated Grade 4 lipase and/or amylase abnormalities that are not associated with symptoms or clinical manifestations of pancreatitis.
 - Isolated Grade 4 electrolyte imbalances/abnormalities that are not associated with clinical sequelae and are corrected with supplementation/appropriate management within 72 hours of their onset.
 - Grade 4 drug-related endocrinopathy adverse events, such as adrenal insufficiency, ACTH deficiency, hyper- or hypothyroidism, or glucose intolerance, which resolve or are adequately controlled with physiologic hormone replacement (corticosteroids, thyroid hormones) or glucose-controlling agents, respectively, may not require discontinuation after discussion with and approval from the BMS Medical Monitor.
- Grade 3 drug-related laboratory abnormalities do **not** require treatment discontinuation except:
 - Grade 3 drug-related thrombocytopenia > 7 days or associated with bleeding requires discontinuation.

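### Drug-related afebrile Grade 4 neutropenia is never a DLT unless G-CSF is given, however long it lasts, and equally long treated episodes are classified by when G-CSF started

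*Combined protocol and SAP*

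**What the plan says.** Section 3.1.6 introduces the definition in general terms: "dose-limiting toxicity (DLT) will be determined based on the incidence, intensity, and duration of AEs that are related to study drug". The lists follow at the end of Section 3.1.6.1, in three separate categories (hepatic, non-hematologic, hematologic), each limited to drug-related events.

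The hematologic list has two neutropenia items. One is febrile neutropenia at Grade 4, whatever its duration. The other is "Grade 4 neutropenia that does not resolve to Grade 3 or less within 5 days of initiation of granulocyte colony stimulating factor (G-CSF". The general item for Grade 3 and above sits in the non-hematologic list and reads "Grade 3 non-hepatic or non-hematologic toxicity with the exceptions noted below".

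On G-CSF itself, Section 3.4.1 puts this among the prohibited treatments: "Use of growth factors unless prior discussion and agreement with BMS Medical Monitor". No section visible in the protocol requires G-CSF for Grade 4 neutropenia or says when to start it. None of the toxicity algorithms named in Section 4.3.2 is hematologic.

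Section 4.3.5 ends treatment for drug-related Grade 4 events, with exceptions that include "Grade 4 neutropenia ≤ 7 days in duration". That limit is measured on the episode, not on G-CSF.

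The DLT definition is used in two ways:
- **Escalation.** Under Section 3.1.1, one DLT among the first evaluable subjects means "additional subjects will be treated in that dose cohort" before any escalation. Section 3.1.3 carries this into Part C with a 4-week window. Section 3.1.6.1 makes a Part C subject evaluable only after at least 2 doses of both drugs. It makes a subject with a dose delay of more than 7 days non-evaluable and replaceable.
- **Expansion.** Section 3.1.4 monitors one pooled rate, over all treated Part D subjects, of treatment-related events that satisfy the DLT definition. The trigger value is redacted.

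**The concern.** A DLT criterion should classify the toxicity. Here the only criterion for afebrile Grade 4 neutropenia is switched on by a supportive-care decision that is optional, has no set timing and needs prior agreement from the Medical Monitor. Two subjects with the same drug-related neutropenia for the same number of days can be recorded differently because one received G-CSF early and the other late or not at all. The subject left without G-CSF cannot be a DLT on any listed criterion.

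DLTs are part of the primary objective and drive both the escalation rule and the Part D safety rate. A prolonged episode that the list cannot see may therefore be missing from both.

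**Working it through.** The plan gives no figure on this point to reproduce, so the check applies the written rules literally.

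**Step 1. Which items can reach a drug-related, afebrile Grade 4 episode?**

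| Item | Reaches it? |
|---|---|
| Febrile neutropenia, Grade 4 | No: requires fever |
| Grade 4 neutropenia, 5 days from G-CSF start | Only if G-CSF is given |
| General Grade 3-or-higher item | No: excludes hematologic toxicity |
| Section 4.3.5, more than 7 days | Ends treatment, but is not a DLT criterion |

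**Step 2. Classification by G-CSF timing.** Let L be the observed length of the episode in days, from onset until it falls to Grade 3 or less. Let d be the days from onset to G-CSF start. The episode is a DLT only if L − d > 5. If G-CSF is never given there is no clock, so it is not a DLT at any L.

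| L (days) | DLT if d is | Not a DLT if d is | Last d that counts | First d that does not |
|---|---|---|---|---|
| 5 | never | any | – | 5 − 0 = 5 |
| 6 | 0 | ≥ 1, or no G-CSF | 6 − 0 = 6 | 6 − 1 = 5 |
| 7 | 0–1 | ≥ 2, or no G-CSF | 7 − 1 = 6 | 7 − 2 = 5 |
| 8 | 0–2 | ≥ 3, or no G-CSF | 8 − 2 = 6 | 8 − 3 = 5 |
| 10 | 0–4 | ≥ 5, or no G-CSF | 10 − 4 = 6 | 10 − 5 = 5 |
| 14 | 0–8 | ≥ 9, or no G-CSF | 14 − 8 = 6 | 14 − 9 = 5 |

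The table compares episodes of equal observed length; early G-CSF may of course shorten an episode. Only episodes of 5 days or less are classified the same way under every G-CSF choice.

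**Step 3. What happens to the uncounted subject in Part C.** Dosing is every 2 weeks, and Table 5.5.1-1 shows pre-dose samples on Days 1, 15 and 29. Take a 10-day episode without G-CSF.
- Onset on Day 10: still present on Day 15 and longer than 7 days, so Section 4.3.5 ends treatment. If the Day 15 dose is not given, the subject has one dose, is non-evaluable and may be replaced.
- Onset on Day 17: two doses have been given, so the subject is evaluable and counts as having no DLT.

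In neither case does the toxicity enter the DLT count.

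**Step 4. Part D rate.** One uncounted event among n treated subjects lowers the pooled rate by 1/n. The number is redacted, so assume n = 20, 40 or 60: 1/20 = 5.0, 1/40 = 2.5 and 1/60 = 1.7 percentage points.

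**Step 5. Evidence to the data cutoff.** Section 1.4.1.5 lists no Grade 3–4 drug-related neutropenia on monotherapy. On the combination, such neutropenia did occur (Sections 1.4.1.5 and 1.4.1.6). Section 1.4.1.8 names four drug-related discontinuation events on the combination (hepatitis, adrenal insufficiency, enterocolitis, pancreatitis), and none is neutropenia. If the current Section 4.3.5 was in force and followed, no drug-related Grade 4 episode had then lasted more than 7 days. This evidence is indirect, and it says nothing about 6- or 7-day episodes.

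**Step 6. Effect of adding a line for more than 7 days from onset.** Every episode with L ≥ 8 becomes a DLT for every d and without G-CSF. L = 6 and L = 7 stay as in the table.

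**The case against.** The strongest reply is that treatment-linked criteria are this protocol's normal pattern. Grade 2 eye events are judged by response to topical therapy, transaminases at 5 to 8 times the upper limit by response to intervention, and a platelet transfusion is a DLT in itself. On this view the G-CSF item deliberately targets neutropenia that resists treatment. That purpose is legitimate, and it is a reason to keep the item. But the eye and transaminase items have backstops that do not depend on treatment: the Grade 3-or-higher item for eye events, and transaminases above 8 times the limit at any duration. Afebrile Grade 4 neutropenia has none.

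The reference to duration in Section 3.1.6 is a general lead-in, and several hematologic items carry no duration at all. This stands: the neutropenia item does not contradict Section 3.1.6.

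The Medical Monitor agrees to G-CSF and, with the Investigators, determines DLTs, so judgement might fill the gap. It might, but no listed criterion would support counting an untreated episode.

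Every such episode still appears in the primary safety endpoint as an adverse event, laboratory abnormality or discontinuation, and Section 4.3.5 protects the subject. Both points stand and limit the harm to the DLT count.

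A reader might also infer that the DLT list and Section 4.3.5 conflict. The documents do not support that, because the protocol separates the two purposes elsewhere. In Section 4.3.5, "Grade 3 drug-related thrombocytopenia > 7 days or associated with bleeding requires discontinuation", while in the DLT list only "Grade 3 thrombocytopenia associated with clinically significant bleeding" counts. Section 4.3.5 shows only that the protocol already has a limit for Grade 4 neutropenia measured on the episode itself.

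**Conclusion.** The gap is real and follows from the written text. Without G-CSF, drug-related afebrile Grade 4 neutropenia of any length is not a DLT; with G-CSF, episodes of 6 days or more are classified by its start day. In escalation the subject is recorded as a non-DLT or becomes non-evaluable and replaceable, so the event can drop out of the dose decision.

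A reader might infer that Part C escalated past a toxic dose or that the Part D dose is wrong. The documents do not support this. No affected case is visible, the Part D dose was selected as well tolerated, and the escalation thresholds are redacted. Nor does the Part D rate force a stop: exceeding it leads to discussion and possible interruption of enrollment.

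The present reach is the Part D aggregate rate, any further Part C cohort and the reported DLT results. No rate of Grade 4 neutropenia is given, so the expected number of affected subjects cannot be estimated; the 5.0, 2.5 and 1.7 points are per event, for assumed denominators. This is a cheap improvement of low-to-moderate priority.

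**What to change.** - **Criterion.** Add to the drug-related hematologic list: *Grade 4 neutropenia lasting > 7 days from onset, whether or not G-CSF is given*. Keep the existing G-CSF item. Keep the drug-related qualifier, because Section 3.3.1 admits subjects with neutrophils as low as 750/µL. The 7 days are taken from Section 4.3.5 as a choice, being the protocol's only limit for Grade 4 neutropenia that does not run from G-CSF start.
- **Evaluability.** State in Section 3.1.6.1 that a subject who meets the new line is DLT-evaluable with a DLT, even if later doses are delayed or stopped.
- **Part D rate.** Compute it under the amended definition for all Part D subjects, past and future, and show the rate under the original definition beside it. Applying the line only to future events would mix two definitions in one numerator.
- **Part C.** List any earlier events that meet the new line, without changing the original determinations.

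The cost is a short amendment and a check of the Part C and D Grade 4 neutropenia records. The DLT count may rise slightly, and two definitions must be reported. Some durations will be approximate, since the blood-count schedule is not visible in the public text. Episodes of 6 or 7 days will still depend on G-CSF timing. The Part D dose does not change.
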